With the exception of AChE inhibitors, the complement inhibitor eculizumab, and a liquid formulation of azathioprine, which have received regulatory approval in Europe for the treatment of gMG, all other existing therapies are used off-label [Vyvgart EPAR].

In the United States (US), efgartigimod is approved for the indication of gMG in adult patients who are AChR antibody positive and in the EU it is approved as an add-on to standard therapy for the treatment of adult patients who are AChR antibody positive.

The recommended dose of efgartigimod is 10 mg/kg as a 1-hour intravenous infusion to be administered in cycles of once weekly infusions for 4 weeks. Subsequent treatment cycles are administered according to clinical evaluation. The frequency of treatment cycles may vary by patient.

In the EU Risk Management Plan (RMP) for efgartigimod, serious infections, is considered to be an important potential risk. As efgartigimod induces a transient lowering in IgG levels, there is a potential

risk for infections associated with the lowered IgG levels. In the randomized placebo-controlled study of 167 patients ARGX-113-1704, 84 patients with gMG were exposed to efgartigimod and the most frequently observed adverse reactions were upper respiratory infections (10.7% in the efgartigimod patients and 4.8% in the placebo patients) and urinary tract infections (9.5% in the efgartigimod patients and 4.8% in the placebo patients). In the patients who received efgartigimod, these events were \leq Grade 2 according to the Common Terminology Criteria for Adverse Events (CTCAE). Overall, treatment emergent infections were reported in 46.4% of patients treated with efgartigimod and 37.3% of patients treated with placebo. The frequency of infections in the efgartigimod treated patients did not increase with repeated cycles of treatment. There were no serious infections or opportunistic infections in the efgartigimod treated patients. This study will evaluate the occurrence of serious infections in gMG patients treated with efgartigimod in the real world setting under conditions of normal clinical practice compared to gMG patients who are not treated with efgartigimod.

During clinical development of the IV formulation, in the efgartigimod phase 3 placebo-controlled 26 week clinical study, ADAPT, there were 2 reported neoplasm events, 1 (1.2%) in the efgartigimod treatment arm and 1 (1.2%) in the placebo treatment arm.

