9. RESEARCH METHODS

9.1 Study Design

This is a non-interventional, prospective, post authorisation safety study.

Patients with gMG who are expected to start treatment with efgartigimod at enrolment or are within their first cycle of efgartigimod at enrolment will be eligible to enrol into the efgartigimod cohort. Patients with gMG who have not been exposed to efgartigimod and for whom it is not planned to start treatment with efgartigimod at enrolment will be eligible to enrol into the non-efgartigimod cohort. It is anticipated that 340 patients will be enrolled in each cohort.

Patients will be treated and observed according to normal clinical practice. Participation in this study does not limit the physicians` clinical decision making as to the most appropriate treatment for the patient during the course of the study. No visits or investigations outside of normal clinical practice will be required. The enrolled patients will be followed prospectively until end of study participation, loss to follow up, consent withdrawal, or death, whichever comes first. All adverse events (AEs) will be collected throughout the duration of the study.

Enrolment of patients will be over a 5-year period. The follow up of patients will continue for 5 years from the time the last patient has been enrolled. Patients will be followed regardless of whether they continue or discontinue efgartigimod. Assuming a 5-year enrolment period this will allow for a maximum of 10 years of follow-up and a minimum of 5 years. A patient will be considered to be an efgartigimod exposed patient if he/she has received at least one dose of efgartigimod.

In order to minimise heterogeneity between the two cohorts, patients in the efgartigimod cohort will be matched at enrollment with a patient in the non-efgartigimod cohort for the following criteria:

- Age (\pm 5 years)
- Myasthenia Gravis -Activities of Daily Living (MG-ADL) score (0-5, 5-9, and >9) ([Wolfe, 1999](#))
- Region (within EU and within US)

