9.2.1 Selection of Study Population

Patients with gMG who are expected to start treatment with efgartigimod at enrolment or are within their first cycle of efgartigimod at enrolment will be eligible to enrol into the efgartigimod cohort. Patients with gMG who have not been exposed to efgartigimod and for whom it is not planned to start

treatment with efgartigimod at enrolment will be eligible to enrol into the non-efgartigimod cohort.

Physicians participating in the study will be instructed to invite all patients who meet study eligibility criteria to enrol until the enrolment period is closed.

Inclusion Criteria (efgartigimod cohort)

1. Patients diagnosed with gMG who are expected to start commercial efgartigimod at enrolment or who are within their first cycle of efgartigimod at enrolment
2. Have provided appropriate written informed consent

Inclusion Criteria (non-efgartigimod cohort)

3. Patients diagnosed with gMG who have not been exposed to efgartigimod and for whom it is not planned to start treatment with efgartigimod at enrolment
4. Have provided appropriate written informed consent

Exclusion Criteria

None

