9.3 Variables

Electronic case report forms (eCRFs) will be specifically designed for the collection of data from this study. An overview of the categories of study variables (raw data) to be collected for each enrolled patient is summarized in [Table 1](#). There may be some missing data if any assessments are not performed as part of normal clinical practice.

Table 1: Study Variables*

Category	Variables	Baseline	Follow up
Confirmation of eligibility, demographics, study status	
 Date of appropriate informed consent for study enrolment Eligibility assessment Demographic characteristics 	✓	
Past and current medical history	
 Relevant medical history including key co-morbidities (including past history of infections) 	✓	

Category	Variables	Baseline	Follow up
	
 Immune status (immunocompromised or immunocompetent) 	✓	✓
gMG Disease	
 Date of diagnosis 	✓	
	
 Criteria used for diagnosis of gMG 	✓	
	
 Antibody status (AChR, MuSK, anti-LRP4)/date 	✓	
	
 Clinical classification (Myasthenia Gravis Foundation of America recommendations) (Jaretzki, 2000) 	✓	✓
	
 Previous myasthenia crises 	✓	
	
 Thymectomy 
 Date Histology 	✓	✓
	
 MG-ADL questionnaire 	✓	✓
Renal function	
 Estimated glomerular filtration rate (eGFR) 	✓ (Most recent prior to initiation of efgartigimod therapy)	✓
gMG treatments in period from diagnosis prior to enrollment (excluding efgartigimod)	
 Drug name, start and stop dates 
 Acetylcholinesterase inhibitors Corticosteroids Other immunosuppressants (specify) Monoclonal antibodies (specify) Plasmapheresis/plasma exchange acute Plasmapheresis/plasma exchange chronic IVIg therapy acute IVIg therapy chronic Other 	✓	

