Balance of the baseline measures, including age, MG-ADL score and region matched at enrollment and other demographic and disease characteristics, will be assessed. The imbalanced measures which are considered to be potential confounders based on clinical judgement will be added to the above base models as covariates. If a large number of imbalanced potential confounders are identified after the enrollment is complete, a propensity score method will be applied instead. More details will be given in the SAP.

Subgroup analyses will be performed using descriptive statistics on the subset of patients who remained on efgartigimod throughout the duration of the PASS. In addition, subgroup analyses of treatment cycle per year or administration per year (four administrations in one cycle if not interrupted), subgroup analyses of time since the last administration of efgartigimod prior to the event occurrence in intervals of every 4 weeks will be performed, and subgroup analysis of patients using efgartigimod as add-on or single treatment will be performed if sample size allows. Since one patient may have multiple same events with different time to the last administration, one patient may be assigned to multiple time intervals.

Events of Interest

Statistical analysis of malignancy and other events of interest will follow the same method as those for serious infections

Exploratory objectives

Descriptive statistics will be used to summarise the long-term safety of efgartigimod for specific subgroups. The number and percentage of patients with AEs/SAEs will be presented. The rate per person-year exposure with a 95% CI will be constructed using asymptomatic normal approximation. This will be done for the following subgroups:

- immunocompromised patients and immunocompetent patients.
- patients treated with monoclonal antibodies and patients not treated with monoclonal antibodies.
- patients who have received live/attenuated vaccine and patients who have not received live/attenuated vaccine.
- patients with moderate to severe renal impairment and patients with normal renal function or mild renal impairment.

Missing values

No imputation will be applied to occurrence of serious infection, malignancy or other safety events.

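### For patients enrolled part-way through their first efgartigimod cycle, the MG-ADL score used for matching and the balance check may be an on-treatment value, because Table 1 anchors only eGFR before the first infusion.

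*Protocol*

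**What the plan says.** Four parts of the Protocol bear on this.

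- **Eligibility (9.2.1).** The efgartigimod cohort takes patients "who are expected to start commercial efgartigimod at enrolment or who are within their first cycle of efgartigimod at enrolment". Section 7 describes efgartigimod as "administered in cycles of once weekly infusions for 4 weeks", so a patient already in the first cycle will normally have had one or more infusions.
- **Matching (9.1).** The rule is that "patients in the efgartigimod cohort will be matched at enrollment with a patient in the non-efgartigimod cohort for the following criteria". The criteria are age, region and the "Activities of Daily Living (MG-ADL) score (0-5, 5-9, and >9" bands.
- **Baseline data (9.3, Table 1).** Baseline eGFR carries the qualifier "Most recent prior to initiation of efgartigimod therapy". The "MG-ADL questionnaire" and the MGFA clinical classification are ticked for baseline and follow-up with no qualifier, and no date is listed for either.
- **Balance check (9.7).** "Balance of the baseline measures, including age, MG-ADL score and region matched at enrollment and other demographic and disease characteristics, will be assessed". Imbalanced measures that are judged potential confounders are added to the logistic and Cox models. If there are many, a propensity score is used instead.

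Section 9.9 expects the more severe patients to be the ones who receive efgartigimod.

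**The concern.** Matching is meant to compare patients of similar severity before the exposure under study. For a patient who enrols mid-cycle, enrolment falls after the exposure has begun. If the score recorded then is used, and the infusions have already lowered it, the patient is placed by the treated score. A patient who started at 11 and scores 7 at enrolment would be paired in the middle band, although the pre-efgartigimod score belongs in the top one.

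Two features make this worth correcting before enrolment. First, the MG-ADL balance check uses the same score that was matched, so it would look satisfactory whether or not pre-efgartigimod severity is balanced. Second, pairs are formed at enrolment, and an analysis plan written later cannot re-form them. If greater severity raises the risk of serious infection, the error inflates the apparent risk of efgartigimod in the primary comparison.

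**Working it through.** **1. Can the score be an on-treatment value?** Matching is timed at enrolment (9.1). Enrolment may follow the first infusion (9.2.1 with Section 7). Table 1 fixes a pre-initiation value for eGFR only. No section asks for a pre-infusion MG-ADL or MGFA class. The Protocol therefore permits an on-treatment score for mid-cycle enrollees, though it does not require one. Patients enrolled before their first infusion are not affected.

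**2. The plan's own figure, for scale.** Section 9.5 gives 84% power for 20% against 31% with 270 per arm. With the unpooled normal approximation, SE = √[(0.20×0.80 + 0.31×0.69)/270] = 0.0372, and 0.11/0.0372 − 1.96 ≈ 1.00, which gives 84.0% (83.7% with a pooled variance). The figure reproduces. It does not depend on MG-ADL, so nothing in the sample size changes. It shows that the study is sized for differences of about 10 to 11 points.

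**3. How many patients could change band?** The documents give no early MG-ADL change, no share of mid-cycle enrolment and no relation between MG-ADL and infection. The following are assumptions:

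- pre-treatment scores are spread evenly over the 15 integers 0 to 14;
- bands are 0-5, 6-9 and above 9 (the printed bands overlap at 5; putting 5 in the middle band gives the same counts);
- every mid-cycle enrollee has the same fall by enrolment;
- 25-50% of the cohort enrols mid-cycle.

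| Fall | Scores that drop a band | Share of mid-cycle enrollees | Share of all pairs at 25% | Share of all pairs at 50% |
|---|---|---|---|---|
| 1 | 6, 10 | 2/15 = 13% | 3% | 7% |
| 2 | 6, 7, 10, 11 | 4/15 = 27% | 7% | 13% |
| 3 | 6-8, 10-12 | 6/15 = 40% | 10% | 20% |
| 4 | 6-9, 10-13 | 8/15 = 53% | 13% | 27% |

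For falls of 2 to 4 points, the range is 0.25×0.267 = 7% to 0.50×0.533 = 27% of pairs.

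**4. What would that do to the risk difference?** Assume further that the true serious-infection risk is 15%, 20% and 25% across the three bands in both cohorts, and that the drug has no effect. Each pair matched one band too low then adds 5 points, so the spurious excess is 0.05 × the share of pairs affected. This gives 0.05×0.067 = 0.3 points to 0.05×0.267 = 1.3 points.

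A simulation with the same gradient used normally distributed scores (mean 7 or 9, SD 3), falls of 1 to 4 points and 25-75% mid-cycle enrolment. It placed about 20-81% of mid-cycle enrollees in too low a band and gave an excess of 0.3 to 3.1 points. With a pre-infusion anchor, or with no early fall, the excess is zero.

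**The case against.** The strongest reply is that 9.1 fixes when patients are matched and leaves the date of the score open. No visit or assessment is required at enrolment (9.2.3), data are abstracted from medical records (9.4), and Table 1 collects only what routine care produces. A site could enter a score recorded before the first infusion. This stands: a reader might infer that every mid-cycle enrollee is matched on a treated score, and the Protocol does not say so.

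Three other stronger readings also fail.

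- **That comparators have milder untreated disease.** Section 8 describes them as treated with other MG medication, so their scores are also recorded on treatment. The documents support only a mismatch with the efgartigimod patient's own pre-efgartigimod severity.
- **That the severity difference would be wholly hidden.** Section 9.7 also checks other disease characteristics. Table 1 records previous crises, earlier gMG treatments and date of diagnosis, none of which a first-cycle infusion alters. These might partly reveal the difference. MGFA class is a weaker safeguard, since it has no pre-dose anchor either.
- **That 11-44% of pairs are affected.** That range comes from spreading scores over 6 to 14 only (4/9 to 8/9 moving, times 25-50%). It leaves out scores of 0 to 5, which cannot drop a band.

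It can also be said that baseline windows are ordinarily left to the eCRF or the SAP. That is fair for model covariates. It is less persuasive for a matching variable, because pairs already formed cannot be revised, and the same table already sets such a window for eGFR.

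**Conclusion.** The point holds as a gap in the definition of baseline. The Protocol allows the only severity matching variable to be measured after exposure has started in some efgartigimod patients, and its MG-ADL balance check cannot detect that.

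The direction of any bias, towards a higher apparent infection risk with efgartigimod, rests on two inferences. One is that early infusions lower MG-ADL, which is plausible for an approved gMG treatment but is not quantified in the documents. The other is that greater severity raises infection risk. The size cannot be determined from the documents. On the illustrative assumptions above it is modest beside the 10 to 11 points the study is sized to detect: it would not by itself create a signal of that size, but it would push in one direction. Correction is worthwhile because the bias is avoidable at little cost.

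**What to change.** In 9.1 and Table 1, define baseline MG-ADL and MGFA class in the efgartigimod cohort as the most recent recorded value before the first efgartigimod infusion, as Table 1 already does for eGFR. For comparators, use the value at enrolment. Record the date of each score; Table 1 already collects efgartigimod administration dates, so timing relative to the first infusion can be derived. Use these values for matching, the balance check and the models.

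For mid-cycle enrollees with no pre-infusion score, do not use the on-treatment score as baseline. Match them on age and region only, treat MG-ADL as missing in the models, and run a sensitivity analysis without them.

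The cost is a wording change in two places and an eCRF instruction with a date field. No visit, test or change in care is needed. The downside is that some patients will have no MG-ADL match; how many depends on routine recording and is not known in advance.

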9.5 Study Size

A sample size of 340 patients in each of the two cohorts is proposed (680 patients in total). Recruitment will be over a 5 year period and patients will be followed for 5 years from the time the last patient is enrolled. Thus maximum follow up will be 10 years.

The estimated prevalence rate for MG is 77.7 per million persons (range 15-179) and the estimated incidence rate is 5.3 per million person-years (range 1.7–21.3).

Myasthenia gravis occurs in both genders, at all ages, and in all races. However, for sample size calculations it is proposed to use the reported serious infection prevalence in MG patients.

Statistical analysis in this study will be descriptive and exploratory, and not aimed to confirm or reject predefined hypotheses.

Sample size calculation is driven by the precision of the estimated incidence proportion of serious infection assuming similar incidence proportion to the background.

In a population-based cohort study of 3823 MG patients ([Kassardjian 2020](#)) followed for a mean of 5.4 (Standard Deviation [SD]=3.8) years, 33.4% of patients experienced a serious infection which included both emergency department visits and hospitalisation with primary diagnosis of infection. In a retrospective chart review of 358 MG patients ([Prior 2018](#)) over a 10-year period, 19% of patients experienced infection. In the argenx-sponsored ADAPT+ study final analysis with 145 efgartigimod patients followed for a mean of 1.7 years (SD=0.7), 6.2% of patients experienced at least one serious infection (serious adverse event with SOC term "Infections and Infestations").

For the current study, serious infection incidence proportion is assumed to be 20% considering varied follow-up time and definitions of serious infection in the literature and argenx-sponsored trial.

The sample size needed to achieve a 5% precision (half-width) is presented in Table 3 below with the following assumptions:

- An incidence proportion of 20% for serious infections among patients receiving efgartigimod.
- Two-sided 95% exact binomial confidence limits based on the Clopper-Pearson method.

Table 3: Precision calculations for different incidence proportions

Number of Patients	Expected Incidence Proportion	Expected Number of Patients with Event*	Lower Limit of 95% Confidence Interval (CI) of Observed Incidence Proportion	Upper Limit of 95% CI of Observed Incidence Proportion
215	15%	32	10.5%	20.5%
245	18%	44	13.4%	23.4%
264	20%	52	15.3%	25.3%

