282	22%	62	17.3%	27.3%
306	25%	76	20.2%	30.2%

*Rounded down to the nearest whole number

A sample size of 270 is recommended to achieve 5% precision (half width). Considering a drop-out rate of 20%, 340 patients in each arm are needed.

To provide further justification about detecting potential increased risk given the calculated sample size above, the power calculation is presented in Table 4 below assuming 20% incidence proportion in the comparator arm and varied increased incidence proportions in the treatment arm with two-sided 0.05 alpha level using normal approximation. With 270 patients who complete the study in each arm, there is 84% power to detect an 11% risk increase.

Table 4: Power calculations to detect potential increased risk

Risk Increase	Expected Proportion for Comparator Arm	Expected Proportion for Treatment Arm	Completion Status	Sample Size in Each Arm	Power
9%	20%	29%	Completers Only	270	69%
10%	20%	30%	Completers Only	270	77%
11%	20%	31%	Completers Only	270	84%
12%	20%	32%	Completers Only	270	89%
9%	20%	29%	Completers + 30 Drop-outs	300	73%
10%	20%	30%	Completers + 30 Drop-outs	300	81%
11%	20%	31%	Completers + 30 Drop-outs	300	88%
12%	20%	32%	Completers + 30 Drop-outs	300	92%
9%	20%	29%	Completers + 60 Drop-outs	330	77%
10%	20%	30%	Completers + 60 Drop-outs	330	85%
11%	20%	31%	Completers + 60 Drop-outs	330	90%
12%	20%	32%	Completers + 60 Drop-outs	330	94%

Owing to the study design with 5-year enrollment and 5-year follow-up, patients will be followed between 5 to 10 years. A discontinued patient enrolled early and discontinued not soon after enrollment will be included in the analysis with possible long follow-up time. For example, the first enrolled patient discontinued at year 6 will have longer follow-up time than the last enrolled patient who has only 5-year

follow-up at maximum. Therefore, early discontinued patient may still contribute high-quality information with acceptable follow-up time to the analysis. Additional power analysis is provided in Table 4 assuming 270 completers +30 and +60 early discontinued patients being included in the analysis, and there is >80% power to detect a 10% risk increase.

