9.7 Data Analysis

The Full Population will be all patients enrolled.

The Safety Population will include all patients enrolled who have taken at least one dose of efgartigimod for the efgartigimod cohort and all patients enrolled into the non-efgartigimod cohort. All analysis will be based on the Safety Population.

Unless otherwise specified, categorical endpoints will be summarised using counts and percent; continuous endpoints will be summarised using mean, standard deviation, median, minimum and maximum values. Statistical analysis will be mainly descriptive in nature using metrics such as

incidence proportion, exposure-adjusted incidence rate, confidence intervals, etc. Details of the analysis plan will be specified in the Statistical Analysis Plan (SAP).

Primary objective

Descriptive statistics will be used to summarise the long-term safety of efgartigimod, including the occurrence of events of serious infections, in gMG patients treated with efgartigimod compared to gMG patients not exposed to efgartigimod. The number and percentage of patients with AEs/SAEs will be presented. The rate per person-year exposure with a 95% CI will be constructed using asymptomatic normal approximation.

Although no formal hypothesis will be tested in the study, statistical models will be used to test the difference of incidence between treatment cohorts (efgartigimod vs. comparator). Two base models which are widely used to model incidence proportion and incidence rate adjusted by potential confounders will be used:

1. To model incidence proportions, a logistic regression model will be used including patients with event vs. patients without event as the response variable and treatment group and country as covariates.
2. To account for varied follow-up time, a Cox regression model will be used with time to the first occurrence of event for each patient as the response variable, treatment group and country as covariates .

Countries with small sample sizes will be combined with other countries based on the geographic locations. Other covariates may be added to the above base models as described below.

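### The cohorts are matched pair by pair, but the base models in 9.7 ignore the pairing and leave out age and MG-ADL when matching succeeds, which probably costs a little power for the serious-infection contrast

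*Protocol*

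**What the plan says.** Section 9.1 (repeated in the Abstract) sets up individual matching: "patients in the efgartigimod cohort will be matched at enrollment with a patient in the non-efgartigimod cohort for the following criteria". The criteria are age (±5 years), MG-ADL band and region. With one partner per patient and equal cohorts of 340, this reads as 1:1 matching.

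Section 9.7 uses two base models to test the cohort difference. The first, for the share of patients with an event, is described thus: "logistic regression model will be used including patients with event vs. patients without event as the response variable and treatment group and country as covariates". For varying follow-up, "a Cox regression model will be used with time to the first occurrence of event for each patient as the response variable", again with treatment group and country. Neither has a pair stratum, cluster or frailty. The same section has baseline measures, expressly including the matched ones, checked for balance. Only those found imbalanced and judged to be confounders are added. If there are many, a propensity score method is used instead.

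On size, section 9.5 says "Sample size calculation is driven by the precision of the estimated incidence proportion of serious infection". Table 4 is offered as additional support, "assuming 20% incidence proportion in the comparator arm" and "with two-sided 0.05 alpha level using normal approximation". Its headline is "With 270 patients who complete the study in each arm, there is 84% power to detect an 11% risk increase".

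**The concern.** Matching on exposure in a cohort study does two things: it balances the matching factors, and it makes partners' outcomes alike to the extent that those factors predict the outcome. The rule in 9.7 deals only with balance. When matching works, age and MG-ADL are balanced and so stay out of the models. The variance is then calculated as if the 2 × 340 patients were independent.

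With positive within-pair correlation, that variance is too large for the difference between cohorts. Intervals are wider than the design warrants and the test is conservative. In a safety study, a conservative test makes a true increase in serious infections easier to report as compatible with no difference.

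**Working it through.** **Inputs from the protocol (9.5, Table 4).** Comparator 20%; efgartigimod 29%, 30% or 31%; 270 completers per arm; two-sided alpha 0.05; normal approximation; 20% drop-out from 340.

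**Input that is assumed.** The within-pair correlation ρ is not in the protocol. A range of 0.01 to 0.18 comes from 400,000 simulated pairs with age SD 16 years, partner age within 5 years, same MG-ADL band and 20% mean risk. The assumed odds ratios were 1.2 to 2.0 per decade of age and 1.0 to 2.0 per MG-ADL band.

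**Step 1: reproduce Table 4.** For independent cohorts, V₀ = p₁q₁ + p₂q₂ = 0.16 + 0.2139 = 0.3739 for 20% versus 31%. SE₀ = √(0.3739/270) = 0.0372. Power = Φ(0.11/0.0372 − 1.96) = Φ(0.996) = 84.0%, the stated figure. The same formula gives all 12 printed powers after rounding, so the table contains no within-pair covariance.

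**Step 2: allow for the pairing.** V(ρ) = V₀ − 2ρ√(p₁q₁·p₂q₂) and SE(ρ) = √(V(ρ)/270).
- True power of the unpaired test: Φ((d − 1.96·SE₀)/SE(ρ)).
- Power of a paired test: Φ(d/SE(ρ) − 1.96).
- True type I error of the unpaired test: 2Φ(−1.96/√(1 − ρ)).

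Example, 20% versus 31% with ρ = 0.18: √(0.16 × 0.2139) = 0.1850, so V = 0.3739 − 0.36 × 0.1850 = 0.3073 and SE = 0.0337. SE₀/SE = 1.103. Unpaired power is 86.4%, paired power 90.3%, a difference of 3.9 points.

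Power with 270 intact pairs, unpaired → paired (difference in points):

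| | ρ = 0.01 | ρ = 0.10 | ρ = 0.18 |
|---|---|---|---|
| 20% vs 31% | 84.2 → 84.4 (0.2) | 85.3 → 87.6 (2.3) | 86.4 → 90.3 (3.9) |
| 20% vs 30% | 77.2 → 77.5 (0.3) | 78.3 → 81.2 (3.0) | 79.3 → 84.6 (5.3) |
| 20% vs 29% | 68.7 → 69.0 (0.3) | 69.5 → 73.1 (3.6) | 70.4 → 77.0 (6.6) |
| Excess of SE₀ over SE | 0.5% | 5% | 10% |
| True type I error | 4.9% | 3.9% | 3.0% |

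A McNemar approximation gives similar losses for 20% versus 31%: about 2 points at ρ = 0.10 and 4 at ρ = 0.20.

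**Step 3: broken pairs.** If partners drop out independently (an assumption), 340 × 0.8 × 0.8 ≈ 218 pairs stay intact among 272 completers per cohort, a share of about 0.8. The effective correlation at the top of the range falls to about 0.8 × 0.18 = 0.144. The losses become 3.2, 4.3 and 5.2 points for 31%, 30% and 29%.

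**Step 4: does covariate adjustment recover the loss?** In a separate simulation of 270 pairs at 20% versus 31%, power was:

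| Assumed odds ratios (age decade / MG-ADL band) | ρ | Unmatched logistic | McNemar | Logistic with age and MG-ADL |
|---|---|---|---|---|
| 1.4 / 1.6 | about 0.07 | 83.9% | 85.7% | 86.1% |
| 1.7 / 2.0 | about 0.15 | 85.3% | 89.5% | 89.8% |

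The paired and adjusted analyses are equivalent within simulation error (about 1 point, from 1,500 and 800 runs). In the stronger scenario the unmatched model's SE was about 7% to 10% above the empirical SE, and its type I error was 3.2%.

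These figures are for proportions. The same direction is expected for the Cox model, but its size was not calculated.

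**The case against.** Variance estimation is ordinarily left to the SAP, and 9.7 defers details there. The section calls these base models and does not exclude clustering. That stands for the choice of estimator. It does not cover the entry rule: the protocol itself fixes the covariates and admits age and MG-ADL only on imbalance, so the stated analysis drops the matching factors when matching succeeds.

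The effect is also small and conditional. The matching bands are broad, country already absorbs most of region, partners need not share an enrolment date or length of follow-up, and drop-out breaks pairs. So does the Safety Population rule, which removes a never-dosed efgartigimod patient but keeps the partner. All of this stands. The issue also overlaps with covariate choice, since adjustment recovers the same gain.

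A reader might infer that the study is underpowered. The protocol does not support that. The 340 comes from single-cohort precision, which pairing does not touch, and under positive correlation even the unpaired test has more power than Table 4 states. A reader might also infer a biased effect estimate, or a large loss from a strong within-pair correlation. Nothing here shows bias, and these matching factors do not plausibly produce a strong correlation. Finally, 9.5 describes the analysis as descriptive and exploratory, although 9.7 still tests the contrast.

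**Conclusion.** The point holds as a minor, conditional loss of efficiency. The protocol pairs patients and then fixes models that use neither the pairs nor, when matching succeeds, age and MG-ADL. The size given above rests on two assumptions: that age and MG-ADL predict serious infection strongly enough to give a within-pair correlation of 0.01 to 0.18, and that 270 pairs stay intact. If the factors do not predict infection, nothing is lost. The loss is measured against a paired or adjusted analysis of the same patients, not against the power that Table 4 states. Table 4 is, if anything, conservative.

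**What to change.** 1. Record a matched-pair identifier at enrolment. The Table 1 overview of variables names none, and a pairing that is not stored may not be recoverable later.
2. In 9.7, always include age and MG-ADL in both base models, whatever the observed balance (country already covers most of region). In addition or instead, use pair-clustered robust variance for the Cox model and GEE with the pair as cluster for proportions. Keep patients without a partner as clusters of one, so that nobody is dropped.
3. Note under Table 4 that it is calculated as if the cohorts were independent.

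The cost is one variable, a few sentences and slightly more analysis work, with no added patients or visits. Once age and MG-ADL are covariates, clustering adds little. Adjustment also makes the odds ratio conditional on those factors: the log odds ratio and its SE rise together while power improves, so the text should say which effect is reported.
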